3.2.4 Intervention content and delivery

We have chosen to name our intervention My Grief My Way following consultation with collaborators, stakeholders, our bereaved persons and Marie Curie Voices PPI groups. Based on the programme theory logic model and data gathered in Phase 1, the research team will determine specific techniques and materials to use in the intervention, and the format this will take (e.g. style, format, timing, order, emphasis, exercises used, type of materials, accessibility, opportunities for user discussion etc.). Materials will include videos, interviews with people about their experience of grieving, readings, poetry, artwork, animation, and audio exercises created and curated for the project such as:

- Stories relating to grief experiences that illustrate common sticking points in grieving.
- Stories that illustrate how the ACT skills of 'be present', 'open up' and 'do what matters', can support grieving, shared via video, audio files and images.
- Metaphors relating to the experience of grief presented via audio and video files
- Exercises which can be completed online or downloaded by the bereaved person
- Mindfulness and similar exercises, delivered via audio files
- Links to psychoeducational resources linked with coping with grief, and other therapeutic approaches including compassion focused therapy and trauma therapy.

• Signposting for bereaved people who feel they need additional support to that offered via the online resources.

We are working with Morrow Communications, a media production company, to develop these resources and make them available online. Our prototype will be user tested by members of our key stakeholder organisations and bereaved persons PPI group. Usability will be assessed by a heuristic evaluation guided by Nielsen's 10 general principles for user interface design (Appendix 15). Bereaved participants will be able to access the resource in a self-directed manner, or with the support of a bereavement support volunteer who has been trained in ACT.

3.2.5 Online access to the intervention materials

Our ACT based bereavement support resource will be hosted on the My Grief My Way website (not yet live). Study participants will be provided with the website link. The site will be live so that site usage data can be collected using Google Analytics and will inform intervention development. The landing page will include a disclaimer so in the unlikely event that the site is found by a member of the public, it will be clear to them that it is part of a research study, and who to contact for further information. The disclaimer will describe the nature of the site, will advise people that the tools and techniques are based on evidence based psychological therapy principles, but that use of a self-help website is not a substitute for professional mental health care. The page will signpost people to their primary care physician for further information and support.

3.2.6 Working through the intervention

Self-directed: Participants who are allocated to work through the intervention themselves will be given a link to the My Grief, My Way website and invited to work through the materials at their own pace for a maximum period of eight weeks.

Bereavement support volunteer facilitated: Participants who are allocated to work through the intervention with additional support from a bereavement support volunteer will be given a link to the My Grief My Way website and invited to work through the materials at their own pace for a maximum period of eight weeks. They will also have access to an ACT-trained bereavement support volunteer, who will provide them with regular ACT-congruent bereavement support for a period of up to six sessions. Six sessions is aligned with the current telephone-based bereavement support offered by our key stakeholder organisations. There is no obligation for the participant to complete all sessions, but they will have this option. The sessions will be provided by bereavement support volunteers within each key stakeholder organisation and will be delivered via the usual platforms used by the key stakeholder organisations.

3.2.7 Option to move from self-directed to volunteer facilitated option

If a participant accessing the MGMW resources in a self-directed manner feels the need for 1:1 support as they work through the intervention, they can inform the research team who will in turn inform the relevant stakeholder organisation that identified them originally. The stakeholder organisation will then allocate the person a bereavement support volunteer who will arrange up to six ACT congruent support sessions with them and the research will continue as planned.

3.2.8 Data collection and analysis

Participant background data: We will collect background information on both groups of participants (i.e., bereavement support volunteers and bereaved participants) so we can describe the sample. For bereavement support volunteers this will include: the organisation for which they volunteer, age, gender, ethnicity, length of time as a bereavement support volunteer in their current organisation, length of time providing bereavement support in their current role and any previous role, whether they have any formal qualifications relevant to their current volunteer role (Appendix 4). For bereaved individuals this will include: the organisation they were referred from; age, gender, ethnicity, relationship to the deceased person, time since most recent bereavement, other types of bereavement support previously or currently accessed (if any). These data will be collected online after they complete the consent form. (Appendix 14). Participants will be given a unique identifier by the research team so that the research team can link their pre and post data (see section 4.1 below).

Qualitative research with bereavement support volunteers: We will run approximately six online focus groups (or semi-structured interviews where focus groups are infeasible) with bereavement support volunteers. We will hold two focus groups after each research cycle. The aim will be to explore volunteer perspectives on the training provided, their experience of delivering ACT-congruent bereavement support, suggestions for resource refinement, and how a facilitated version of the intervention can be delivered in practice. We will also explore their perspectives on training for new facilitators and views on sustaining the intervention in the long term. Participants can only take part in one focus group per cycle, but may take part in more than one focus group across cycles (i.e., up to three in total). See topic Guide in Appendix 16. Focus groups/interviews will be audio recorded, transcribed, and anonymised by a member of the research team. Data will be analysed using rapid qualitative analysis techniques²⁸ informed by a framework approach and results following each cycle will feed into intervention delivery and content creation for the subsequent cycle.

My Grief My Way study protocol FINAL V2 25 September 2023

Qualitative research with bereaved participants: Participants will be invited to take part in focus groups or individual semi-structured interviews if preferred. The aim of the focus groups will be to explore their experience of accessing the My Grief My Way resource, and any impacts it might have had on them, as well as giving us feedback about the materials. We will hold 2 to 3 focus groups after each cycle, depending on participant availability. Semi-structured interviews will be conducted where a participant cannot or prefers not to take part in a focus group. See topic Guide in Appendix 17. Focus groups/interviews will be conducted at a mutually agreed time via Microsoft Teams (or by telephone if preferred). These will be audio recorded, transcribed, and anonymised by a member of the research team. Data will be analysed using rapid qualitative analysis techniques²⁸ informed by a framework approach and results following each cycle will feed into intervention delivery for the subsequent cycle.

Intervention module usefulness: Bereaved participants' perspectives on intervention module usefulness (n = 30-45): This will be accessed by participants via a feedback icon on each module webpage. By clicking on the icon, participants will be asked an open question on the usefulness of the module they have completed. Data will be imported into NVivo and analysed thematically following each cycle, and the findings will be used to refine the intervention prior to subsequent iterations.

Intervention engagement will be assessed via routine website activity collected via Google Analytics. This will include the times each webpage was accessed, amount of time on each webpage, downloads of materials from the website etc. We will analyse this data after each research cycle to assess the relative usage of different intervention components, and estimate levels of engagement.

Intervention feasibility and effect size estimates: Data to inform future feasibility and effectiveness studies will include bereaved participant and volunteer **recruitment** and **retention rates** throughout the intervention. We will also collect data using validated measures of coping with grief, well-being and quality of life in order to determine the feasibility of data collection for future studies, and to explore effect size estimates for use in the design of future evaluations studies. (Appendices 7-13) These measures will be administered by online questionnaires, and completion can be supported by the research team via telephone or Microsoft Teams depending on participant preference. Outcome data will be collected at baseline (i.e., following consent, but prior to accessing the intervention) and at the end of the intervention (i.e., approximately eight weeks post commencement of the intervention).

Measures

Ato Grief scale (AAG).⁽⁸⁾ This scale provides a profile of how people are responding to their grief along three dimensions: overwhelmed, overly controlled or resilient. Together these processes are thought to reflect a person's vulnerability to complicated grief and/or prolonged grief reactions.⁽⁹⁾ The AAG is a 9-item Likert scale inviting responses from strongly agree to strongly disagree. Maximum score =36 where vulnerability is assessed as follows: Severe vulnerability >24, High vulnerability >21-23, Low vulnerability < 20. (Appendix 7)

ICECAP-A (Health Economics).⁽³²⁾ ICEpop CAPability measure for Adults is a measure of capability for the general adult (18+) for use in economic evaluation. ICECAP-A focuses on wellbeing defined in a broader sense, rather than just health. The measure covers attributes of wellbeing that were found to be important to adults in the UK: 1. Feeling settled and secure. 2. Love, friendship and support. 3. Being independent. 4. Achievement and progress. 5. Enjoyment and pleasure. Responses range from one to four on a Likert scale. A score of one represents poor quality of life, with four indicating good quality. (Appendix 8)

EQ-5D-5L ⁽³³⁾ consists of 2 pages: the EQ-5D descriptive system and the EQ visual analogue scale (EQ VAS). The descriptive system comprises five dimensions: mobility, self-care, usual activities, pain/discomfort and anxiety/depression. Each dimension has five levels: no problems, slight problems, moderate problems, severe problems and extreme problems. The patient is asked to indicate his/her health state by ticking the box next to the most appropriate statement in each of the five dimensions. (Appendix 9)

Inventory of Daily Widowed Life - Modified (IDWL-M).⁽¹⁰⁾ IDWL is a 22-item questionnaire that measures oscillation between two coping processes from the Dual Process Model of Coping with Bereavement Loss-orientation (LO) and restoration-orientation (RO).⁽¹¹⁾ Questions are evenly divided between the two categories. LO and RO scores range from 11 (low) to 44 (high). Oscillation Balance = RO score minus LO score (possible range =-33 (exclusively loss-oriented) to +33 (exclusively restoration-oriented). A score equal to zero (0) indicates perfect oscillation balance. Oscillation between RO and LO activities are considered to be an indicator of healthy, effective grieving, whilst remaining predominantly in one or other orientation is considered to be potentially problematic.

Originally worded to reflect spousal loss, the modified version has had minor rewording to reflect the loss of any loved one and has ben psychometrically validated. (Appendix 10) ⁽³⁴⁾

Inventory of Social Support (ISS).⁽¹⁹⁾ The 5-item instrument was developed from qualitative data obtained from bereaved adolescents who provided written responses to the questions "What helped you cope with your grief?" and "What made it harder for you to cope with your grief?" Items are scored using a 5-point Likert scale, where respondents are asked to use the prior two weeks as a time scale when rating each item. Response values are added then divided by the number of items. Response values represent the degree to which a bereaved person feels supported in the context of their world. (Appendix 11)

Psychological-Flexibility.⁽³⁵⁾ This 6-item questionnaire is a short self-report measure that covers all facets of psychological flexibility construct: The ability to be aware of and open to internal and external stimuli as they occur while choosing to act in ways that are consistent with what a person deeply cares about. Each item is scored from 1-5, one indicating low flexibility and five representing high flexibility.⁽¹⁸⁾ (Appendix 12)

Warwick-Edinburgh Mental Wellbeing Scale (WEMWBS).⁽¹²⁾ Developed to monitor mental wellbeing in the general population; this 14-statement questionnaire has five response categories from 'none of the time' to 'all of the time'. Scores range from 14-70. Higher scores indicate good mental wellbeing. The WEMWBS responsiveness to change has been evaluated at both population and individual level, which shows that a change of three or more points can be considered significant.⁽¹³⁾ (Appendix 13)

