3.1 Study design overview

This 24-month study will follow recent guidance on intervention development,⁽¹⁹⁾ informed by the person-centred approach to intervention development, and set within the MRC framework.⁽²⁰⁾ Person centred approaches are particularly relevant to the development of online interventions as people typically use these independently, so the intervention needs to be designed in a format that maximises

engagement and accessibility. Central to the person-centred approach is the idea that behaviour change interventions should promote autonomy, competence, and a positive experience - these design objectives will guide our intervention development process.⁽²¹⁾

In Phase 1, we will develop a programme theory to illustrate how an online ACT based bereavement support intervention could lead to improved coping, quality of life and wellbeing following bereavement. This will be informed by : (i) relevant theory and evidence from existing literature reviews; (ii) a rapid review of the literature regarding the feasibility and effectiveness of online bereavement support (iii) views of therapists on how ACT is used for bereavement support; (and iv) feedback from stakeholders and people with lived experience of bereavement. We have recently completed Phase 1.

In Phase 2, we will design the intervention prototype. The intervention will be delivered in one of two ways: **(i) Self-directed:** Whereby people seeking bereavement support can access the materials free of charge in a flexible manner. Or **(ii) Volunteer facilitated:** Whereby people seeking bereavement support will access the online bereavement support materials and also have access to a bereavement support volunteer, who will provide ACT congruent bereavement support. We will train current bereavement support volunteers in ACT so they can provide ACT-congruent support. The intervention (both self-directed and facilitated) will then be delivered to bereaved participants and refined iteratively using rapid qualitative^(22, 23) and mixed method designs.⁽²⁴⁾

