3.2.1 Design

We will use rapid qualitative and mixed methods design to test and refine the prototype over a series of three rapid iterations. Each cycle will involve bereaved participants working through the intervention individually or with the support of a bereavement support volunteer, and providing feedback on content, format, and usefulness. We will also gather feedback from bereavement support volunteers involved in intervention delivery.

3.2.2 Participant recruitment Bereavement support volunteers:

We aim to recruit approximately 20 bereavement support volunteers and professional staff currently providing bereavement support through our collaborator organisations, Marie Curie and Cruse Scotland. A target sample size of approximately 20 was chosen based primarily on pragmatic considerations in consultation with our key stakeholder organisations. We will train two groups of volunteers. In our experience, group sizes of about ten participants tend to work well in allowing opportunities for participants to get to know each other and contribute to the discussion.

Bereavement support service managers at Marie Curie and Cruse Scotland will share study information and the participant information sheet (bereavement support volunteer version) (Appendix 2) with their current bereavement support volunteers via team meetings, regular bulletins disseminated via email and their usual organisation communication platform(s). Volunteers will be eligible to participate if they meet the following criteria: (i) have completed Marie Curie or Cruse Scotland bereavement support training; (ii) have been actively supporting bereaved clients at Cruse or Marie Curie for at least one year; and (iii) speak English fluently. We will exclude student volunteers who are on placement with key stakeholder organisations for continuity purposes. If a volunteer is interested in taking part, they can either contact the research team directly for further information, or they can give their manager permission to send their contact details to the research team. A member of the research team will then contact them via email, Microsoft Teams or telephone if they prefer, to answer any questions they may have. If they want to sign up, a member of the research team will email the volunteer a link to the online consent form. Having completed the online consent from, (Appendix 3) the participant will then be directed to complete a short background questionnaire

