- Where **Cruse Scotland** decides that a client would benefit from one-to-one bereavement support (in line with their usual assessment in-house protocols), the assessing practitioner will inform the client of the My Grief My Way study (**facilitated option**) and give the participant

information sheet. (Appendix 5) This process will be coordinated by [name], Director of Client Services at Cruse Scotland. Interested participants will be directed to the research team to find out more and consent to take part should they wish (or with their permission, their name and contact details will be passed to the research team). If they do not wish to find out about the study, they will be allocated a to a Cruse bereavement support volunteer as normal. If they do decide to take part in the study, they will complete an online consent form and baseline assessments. (Appendix 6 and Appendices 7-13 respectively) The research team will then inform Cruse that the client has been recruited. Cruse will allocate an ACT-trained volunteer to the research participant, who will contact them and arrange weekly or fortnightly meetings by telephone or other preferred means for up to six sessions (in line with usual practice).

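### Uncontrolled eight-week change in a prototype still being refined cannot supply the between-arm effect size needed to design a later trial

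*Protocol*

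**What the plan says.** Section 3.2.8 (Intervention feasibility and effect size estimates) gives the validated measures two purposes. One is to learn whether the data can be collected. The other is "to explore effect size estimates for use in the design of future evaluations studies". On timing it says: "Outcome data will be collected at baseline (i.e., following consent, but prior to accessing the intervention) and at the end of the intervention", the latter being "approximately eight weeks post commencement of the intervention".

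No group goes without the intervention. Section 3.1 says: "The intervention (both self-directed and facilitated) will then be delivered to bereaved participants and refined iteratively". Section 3.2.1 plans to "test and refine the prototype over a series of three rapid iterations", and section 3.2.8 says of the module feedback that "the findings will be used to refine the intervention prior to subsequent iterations". Section 3.2.2 sets 30-45 bereaved participants in total, 10-15 per cycle.

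Delivery mode is not randomised. At Cruse Scotland it follows triage and assessed need; at Marie Curie it follows which telephone service the person called (section 3.2.2). Section 3.2.7 lets self-directed participants move to volunteer support. Cruse clients assessed for one-to-one help who do not want to hear about the study are dealt with thus: "they will be allocated a to a Cruse bereavement support volunteer as normal" (section 3.2.2). Section 3.2.6 says the limit of six sessions matches the telephone support the partner organisations already offer.

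The protocol does not say whether effect sizes will be pooled or split by cycle or mode, and it adds no caution about reading them as treatment effects.

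**The concern.** A later controlled evaluation would test a difference between arms, for one finished version delivered in one defined way. This study yields a before-after difference in people who all received a developing version. The two quantities differ for four reasons:

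- **Natural adjustment.** Section 1.1 describes grieving as a natural process in which most bereaved people adjust. Some improvement over eight weeks is plausible without any intervention.
- **Regression to the mean.** People enter when they contact a service for help, which may be when they feel worst.
- **Support like that usually offered.** Many facilitated participants come through routes where volunteer sessions are already the normal offer. Their change may therefore include the benefit of ordinary support.
- **No single intervention.** Content changes between cycles and is finalised only at the workshop in section 3.2.9. Mode is tied to need or to the service contacted.

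The cost would fall on the next study. If this change were carried into a sample-size calculation as the expected difference, that trial could be badly underpowered.

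**Working it through.** **The plan's own figure.** Three cycles of 10-15 give 3 × 10 = 30 to 3 × 15 = 45, as stated. The protocol gives no alpha, power, target effect, SD, correlation or dropout rate, so nothing else can be reproduced. What follows is illustration on stated assumptions.

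**Precision.** Assume 80% follow-up, a change of d = 0.4 baseline SDs and a pre-post correlation r of 0.5 to 0.7.

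- Completers overall: 0.8 × 30 = 24 to 0.8 × 45 = 36. Completers per cycle: 0.8 × 10 = 8 to 0.8 × 15 = 12.
- SE = √[2(1 − r)/n + d²/(2n)]; 95% half-width = t(0.975, n − 1) × SE.

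| Completers | r | SE | t | Half-width |
|---|---|---|---|---|
| 24 | 0.5 | 0.212 | 2.069 | 0.44 |
| 36 | 0.7 | 0.137 | 2.030 | 0.28 |
| 8 | 0.5 | 0.367 | 2.365 | 0.87 |
| 12 | 0.7 | 0.238 | 2.201 | 0.52 |

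For one cycle the half-width exceeds the assumed effect of 0.4 throughout. For all completers it runs from about 70% of that effect (0.28/0.4) to slightly more than all of it (0.44/0.4).

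A second method gives the same picture. It uses the noncentral t interval for change divided by the SD of change, with no dropout. For an observed 0.5 the 95% interval is 0.12 to 0.88 at n = 30 and 0.19 to 0.81 at n = 45. For one cycle it is −0.17 to 1.15 at n = 10 and −0.05 to 1.03 at n = 15.

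**Scaling.** With equal variances, change divided by the SD of change equals change divided by the baseline SD, multiplied by 1/√[2(1 − r)]. The multiplier is 1.00 at r = 0.5 and 1.29 at r = 0.7. One dataset therefore gives different effect sizes according to the divisor.

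**Consequence for a later trial.** Suppose a 1:1 trial is sized on an observed change of 0.5 SD with a two-sided 5% t-test and 80% power. It needs 64 per arm. Let part of the 0.5 be change that would also occur in the control arm. The between-arm effect is then 0.5 minus that part. Power at 64 per arm comes from the noncentral t distribution with 126 degrees of freedom and noncentrality effect × √(64/2).

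| Natural change (assumed) | Between-arm effect | Noncentrality | Power at 64 per arm | Per arm for 80% |
|---|---|---|---|---|
| 0 | 0.5 | 2.83 | 80% | 64 |
| 0.1 | 0.4 | 2.26 | 61% | 100 |
| 0.2 | 0.3 | 1.70 | 39% | 176 |
| 0.3 | 0.2 | 1.13 | 20% | 394 |
| 0.4 | 0.1 | 0.57 | 9% | 1,571 |

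**What the design can estimate.** An SD needs no comparator. Its 95% interval is the estimate times √[(n − 1)/χ²], that is 0.80 to 1.34 times the estimate at n = 30 and 0.83 to 1.26 at n = 45. That is wide, but it is an interval for the right quantity.

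**The case against.** The strongest reply is that this is a development study with a modest clause. The verb is explore. Effect size appears in none of research questions 2a to 2d, no efficacy claim is made, and the protocol does not say that observed change will be entered in a sample-size formula. It also foresees feasibility work before any full evaluation. In section 1.1 the authors say of another small feasibility study that effectiveness could not be established, so they know the issue.

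This limits the weight. The study's qualitative and feasibility conclusions are untouched. But the sentence does name the use, the design of later evaluation studies, and no caveat follows. An analysis plan could settle how results are split; it cannot supply a comparator.

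Several stronger readings are tempting but unsupported:

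- **That results will be pooled over cycles and modes.** Nothing says so, and the choice may properly sit in an analysis plan.
- **That outcomes will be picked by largest change.** Section 3.2.9 gives prioritisation to a workshop of stakeholders, public contributors and researchers.
- **That all facilitated participants would have had a volunteer anyway.** The Cruse sentence concerns clients who do not want to hear about the study, and some facilitated participants may have switched from the self-directed route.
- **That the effect is certainly inflated, by a known amount.** Upward bias is plausible from section 1.1, but no size or eight-week time course is given.
- **That the WEMWBS statement, "a change of three or more points can be considered significant", sets a between-group target.** It describes responsiveness to change and does not define a minimum important difference between arms.

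**Conclusion.** The concern holds for the stated use of the effect sizes. With no comparator, the design gives uncontrolled within-person change, which is not the between-arm effect a later trial would test. That conclusion follows from the design and needs no numerical assumption.

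The sizes do rest on assumptions. The imprecision depends on the assumed follow-up, correlation and standardised change. The power loss depends wholly on the assumed natural change, so the full range in the table should be read rather than any single row.

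This should be corrected because the stated aim promises something the data cannot deliver. It does not invalidate the study.

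**What to change.** In section 3.2.8:

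1. Replace the effect-size aim with estimating, with 95% confidence intervals, each measure's SD, pre-post correlation and completion, alongside recruitment and retention.
2. Report mean change by cycle and by delivery mode descriptively, labelled as uncontrolled within-person change. Give the divisor if it is standardised.
3. State that this change will not be taken as the assumed between-arm effect in a future sample size, which should rest on a justified important difference or on controlled evidence. The measure and its target difference can be left to the team designing that trial.

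The cost is a few sentences and minor analysis. No extra participants, data or visits are needed. The one downside is a less ambitious aim.
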